2.5 Supportive secondary endpoints

2.5.1 Efficacy endpoints

For the following continuous supportive efficacy endpoints, analyses similar to those for the primary estimand of the primary endpoint will be done, with the adjustment that the non-inferiority-penalty (NI-penalty) in step five of multiple imputation is not applied (this is only considered

relevant for non-inferiority testing). Continuous safety endpoints that are analysed statistically will also follow this procedure. A further change to the above specified model is that the model will include the baseline measurement of the endpoint as a covariate instead of the baseline HbA_{1c} measurement.

The following supportive secondary endpoints will be analysed through the statistical analysis described above.

HbA_{1c}

Change from baseline in HbA_{1c} (%) after 38 weeks.

In addition to the analysis specified for the primary estimand, the analysis specified for the secondary estimand will also be performed for this endpoint to align with analysis of HbA_{1c} after 26 weeks.

Fasting plasma glucose

- Change from baseline in FPG after 26 weeks
- Change from baseline in FPG after 38 weeks

Self-measured plasma glucose measurements (SMPG)

- **SMPG after 26 weeks**
 - Change from baseline in mean pre-breakfast measurements after 26 weeks
 - Change from baseline in post-prandial increments after 26 weeks
- **SMPG after 38 weeks**
 - Change from baseline in mean pre-breakfast measurements after 38 weeks
 - Change from baseline in post-prandial increments after 38 weeks

Furthermore, the mean PG before breakfast used for dose-titration and the 9-point profile will be calculated at each visit using the available data.

Responder for HbA_{1c}

- **Responder (Yes/No) for HbA_{1c} after 26 weeks:**
 - HbA_{1c} < 7%
 - HbA_{1c} < 7% without severe or BG confirmed symptomatic hypoglycaemia
- **Responder (Yes/No) for HbA_{1c} after 38 weeks:**
 - HbA_{1c} < 7%
 - HbA_{1c} < 7% without severe or BG confirmed symptomatic hypoglycaemia

Subjects with less than 16 weeks of treatment will be set as non-responders. Hypoglycaemic episodes will be based on the available data.

Analysis of each of the responder endpoints will be based on a logistic regression model which will include treatment, sex, previous insulin treatment regimen, previous OAD treatment and region as fixed factors, and age and baseline HbA_{1c} as covariates. The analysis for the responder endpoints will be derived using the HbA_{1c} values from the 1000 datasets originating from multiple imputation analysis of HbA_{1c}, without applying the NI-penalty.

Each of these datasets will be analysed using the above logistic regression model and the results will then be pooled using Rubin's rule.

Explorative endpoints

The following endpoint will be analysed through the same statistical analysis for continuous endpoint:

- SMPG after 38 weeks
 - Change from baseline in post-prandial increments after 38 weeks
- Change from baseline to week 26 for:
 - Health-related quality of life as evaluated by SF-36v2® Health Survey
 - Treatment related impact as evaluated by the Treatment Related Impact Measure-Diabetes (TRIM-D)
- Change from baseline to week 38 for:
 - Health-related quality of life as evaluated by the SF-36v2® Health Survey
 - Treatment related impact as evaluated by the TRIM-D

Assessments

The following efficacy assessments will be summarised descriptively but with no statistical analyses performed:

- Responder (Yes/No) for HbA_{1c} after 26 weeks:
 - HbA_{1c} < 7% without nocturnal (00:01-05:59) severe or BG confirmed symptomatic hypoglycaemia
- Responder (Yes/No) for HbA_{1c} after 38 weeks:
 - HbA_{1c} < 7% without nocturnal (00:01-05:59) severe or BG confirmed symptomatic hypoglycaemia

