8.5.2 Laboratory assessments for efficacy

8.5.2.1 HbA_{1c}

The HbA_{1c} result taken at the screening visit (V1) must be available prior to the randomisation visit (V2).

HbA_{1c} is measured regularly during the trial in order to assess glycaemic control and sites will receive individual HbA_{1c} reports for each subject to be used for evaluation and subject training purposes in relation to insulin dose adjustment.

For subjects prematurely discontinuing trial product abbreviated visits (V28a and V40a) should be scheduled at the dates of the originally planned visit 28, if applicable and visit 40 in order to collect samples for HbA_{1c} analysis – refer to flow chart (Section [2](#)).

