17.5 Supportive secondary endpoints

17.5.1 Efficacy endpoints

For the following continuous supportive efficacy endpoints, analyses similar to those for the primary and secondary estimands of the primary endpoint will be done, with the adjustment that the non-inferiority-penalty (NI-penalty) in step five of multiple imputation is not applied (this is only considered relevant for non-inferiority testing). Continuous safety endpoints that are analysed

statistically will also follow this procedure. A further change to the above specified model is that the model will include the baseline measurement of the endpoint as a covariate instead of the baseline HbA_{1c} measurement.

HbA_{1c}

Change from baseline in HbA_{1c} (%) after 38 weeks.

Fasting plasma glucose

- Change from baseline in FPG after 26 weeks
- Change from baseline in FPG after 38 weeks

Self-measured plasma glucose measurements (SMPG)

- **SMPG after 26 weeks**
 - Change from baseline in mean pre-breakfast measurements after 26 weeks
 - Change from baseline in post-prandial increments after 26 weeks
- **SMPG after 38 weeks**
 - Change from baseline in mean pre-breakfast measurements after 38 weeks
 - Change from baseline in post-prandial increments after 38 weeks

Furthermore, the mean PG before breakfast used for dose-titration and the 9-point profile will be calculated at each visit using the available data.

Responder for HbA_{1c}

- **Responder (Yes/No) for HbA_{1c} after 26 weeks:**
 - HbA_{1c} < 7%
 - HbA_{1c} < 7% without nocturnal (00:01-05:59) (BG) confirmed symptomatic hypoglycaemia
- **Responder (Yes/No) for HbA_{1c} after 38 weeks:**
 - HbA_{1c} < 7%
 - HbA_{1c} < 7% without nocturnal (00:01-05:59) BG confirmed symptomatic hypoglycaemia

Subjects with less than 16 weeks of treatment will be set as non-responders. Nocturnal hypoglycaemic episodes will be based on the available data.

Analysis of each of the responder endpoints will be based on a logistic regression model which will include treatment, sex, previous insulin treatment regimen, previous OAD treatment and region as fixed factors, and age and baseline HbA_{1c} as covariates.

The primary estimand for the responder endpoints will be derived using the HbA_{1c} values from the 1000 datasets originating from multiple imputation analysis of HbA_{1c}, without applying the NI-penalty. Each of these datasets will be analysed using the above logistic regression model and the results will then be pooled using Rubin's rule.

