2.1 Primary and secondary estimands

The primary estimand will be the difference in change from baseline at week 26 or week 38 depending on the endpoint considered between IDegAsp OD and IGlar OD + IAsp OD, for all randomised subjects regardless of whether the subjects remained on initially assigned treatment until week 26 or week 38. This estimand is a de facto estimand addressing effectiveness.

The secondary estimand will be the difference in change from baseline at week 26 or week 38 depending on the endpoint considered between IDegAsp OD and IGlar OD + IAsp OD if all randomised subjects had adhered to treatment until week 26 or week 38. This estimand is a de jure estimand addressing efficacy.

For hypoglycaemic episode endpoints, only the de jure estimand will be used. The reason for this is that data for hypoglycaemic episodes will not be systematically collected after treatment discontinuation.

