2.4 Primary endpoint

Primary statistical analysis for primary estimand

The primary estimand will be estimated based on the FAS using all post baseline HbA_{1c} measurements obtained on planned visits up until week 26, including week 26 measurements from subjects withdrawing from randomised treatment (in-trial observation period), mimicking an ITT scenario. To estimate this estimand for evaluation of non-inferiority of HbA_{1c}, multiple imputation of missing values with separate imputation from each treatment arm will be applied. The use of data from prematurely treatment discontinued subjects in analyses will equalise treatment effects and the inclusion of a penalty equal to the non-inferiority margin will remedy this. Imputation will be done as follows:

- In the first step, intermittent missing values are imputed using a Markov Chain Monte Carlo (MCMC) method, in order to obtain a monotone missing data pattern. This imputation is done for each treatment arm separately and 1000 copies of the dataset will be generated.
- In the second step, for each of the 1000 copies of the dataset, an analysis of covariance (ANCOVA) for each treatment arm with region, sex, previous insulin regimen and previous OAD treatment as categorical fixed effects and baseline HbA_{1c} measurement and age as a covariate will be fitted to the change in HbA_{1c} from baseline to week 8 (visit 10). The estimated parameters and their variance from this model are used to impute missing values at week 8 for subjects in the respective treatment arms based on region, sex, previous insulin regimen, previous OAD treatment, age and HbA_{1c} at baseline.
- In the third step, for each of the 1000 copies of the dataset, an analysis of covariance model with region, sex, previous insulin regimen and previous OAD treatment as categorical fixed effects, and age, baseline HbA_{1c} and HbA_{1c} at week 8 (Visit 10) as covariates is fitted to the change in HbA_{1c} from baseline to week 12 (Visit 14) for each treatment arm. The estimated parameters and their variances from this model are used to impute missing values at week 12 for subjects in the respective treatment arms, based on region, sex, previous insulin regimen, previous OAD treatment, age and HbA_{1c} at baseline and week 8.
- Step three is repeated over the available planned visits, adding one visit at a time until week 26. In each step the model is expanded to include a covariate from the previous visit.

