3.4 Statistical analyses of the following assessments will not be performed

Efficacy assessments:

- $\text{HbA}_{1c} < 7\%$ without nocturnal (00:01-05:59) severe or BG confirmed symptomatic hypoglycaemia after 26 weeks
- $\text{HbA}_{1c} < 7\%$ without nocturnal (00:01-05:59) severe or BG confirmed symptomatic hypoglycaemia after 38 weeks

Safety assessments:

- Number of nocturnal, treatment-emergent severe or BG confirmed hypoglycaemic episodes during 26 weeks
- Number of treatment-emergent severe or BG confirmed hypoglycaemic episodes during 26 weeks
- Number of nocturnal, treatment-emergent severe or BG confirmed hypoglycaemic episodes during maintenance (week 16-26)
- Number of treatment-emergent severe or BG confirmed hypoglycaemic episodes during maintenance (week 16-26)
- Number of nocturnal, treatment-emergent severe or BG confirmed hypoglycaemic episodes during 38 weeks
- Number of treatment-emergent severe or BG confirmed hypoglycaemic episodes during 38 weeks

All above assessments will be summarized descriptively.

Rationale:

These assessments are supportive and no statistical analyses are needed.

3.5 Statistical analyses based on the secondary estimand will not be performed for the following endpoints

Efficacy endpoints:

- Change from baseline in FPG after 26 weeks
- Change from baseline in FPG after 38 weeks
- Change from baseline in mean pre-breakfast measurements after 26 weeks
- Change from baseline in post-prandial increments after 26 weeks
- Change from baseline in mean pre-breakfast measurements after 38 weeks
- Change from baseline in post-prandial increments after 38 weeks
- Responder (Yes/No) for $\text{HbA}_{1c} < 7\%$ after 26 weeks
- Responder (Yes/No) for $\text{HbA}_{1c} < 7\%$ without severe or BG confirmed symptomatic hypoglycaemia

- Responder (Yes/No) for $\text{HbA}_{1c} < 7\%$ after 38 weeks
- Responder (Yes/No) for $\text{HbA}_{1c} < 7\%$ without severe or BG confirmed symptomatic hypoglycaemia after 38 weeks

Safety endpoints:

- Change in weight from baseline to week 26
- Change in weight from baseline to week 38

Rationale:

For the above endpoints only the primary estimand are relevant.

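### The 16-week non-responder rule overrides measured HbA1c, so the HbA1c <7% responder analyses are an undeclared hybrid under a de facto label

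*SAP*

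**What the plan says.** SAP 2.1 defines the primary estimand "for all randomised subjects regardless of whether the subjects remained on initially assigned treatment until week 26 or week 38" and adds: "This estimand is a de facto estimand addressing effectiveness".

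The HbA1c <7% responder endpoints at weeks 26 and 38 are assigned to that estimand twice. Protocol 17.5.1 states: "The primary estimand for the responder endpoints will be derived using the HbA_{1c} values from the 1000 datasets". SAP 3.5 lists these endpoints among those for which the secondary-estimand analysis is dropped, with the reason: "For the above endpoints only the primary estimand are relevant".

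The data for such an analysis are planned. Subjects who stop trial product are to be retained (protocol 6.6), and for them "abbreviated visits (V28a and V40a) should be scheduled at the dates of the originally planned visit 28" and visit 40, to sample HbA1c (protocol 8.5.2.1). The imputation in SAP 2.4 uses in-trial HbA1c, including week 26 values obtained after stopping treatment. SAP 2.5.1 takes responder status from there: "The analysis for the responder endpoints will be derived using the HbA_{1c} values from the 1000 datasets originating from multiple imputation analysis", without the non-inferiority penalty.

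The same SAP section, like protocol 17.5.1, also says: "Subjects with less than 16 weeks of treatment will be set as non-responders". The sentence is not limited to subjects with missing HbA1c and makes no exception for values retrieved after discontinuation.

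**The concern.** The assigned estimand disregards whether a subject stayed on treatment; the 16-week rule makes the outcome depend on exactly that. Take two subjects with a V28a HbA1c of 6.5%, one stopping at week 15 and the other at week 17. The first is a failure and the second a responder, although the continuous HbA1c analysis uses 6.5% for both. The same cut serves week 38, where the subject who stopped at week 17 is classified on a value taken about 21 weeks later (38 − 17).

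Both HbA1c <7% endpoints are key supportive endpoints selected for public disclosure (protocol 4.2.2.1), and each will be reported with an odds ratio. The trial is open-label with different regimens, so unequal early stopping is possible. If it occurs, the odds ratio will partly reflect stopping rather than the HbA1c achieved. No responder analysis without the rule is planned in either document.

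**Working it through.** **1. The texts side by side.** For a subject with a measured V28a or V40a value:

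| Time of stopping | Assigned estimand (SAP 2.1, 3.5) | Rule in SAP 2.5.1 |
|---|---|---|
| Before 16 weeks of treatment | Use the HbA1c value | Non-responder whatever the value (composite strategy) |
| After 16 weeks of treatment | Use the HbA1c value | Use the HbA1c value (treatment policy) |

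If the value is missing, the imputed one takes its place, and the rule overrides that too for early stoppers. The conflict is therefore in the text and needs no calculation. Only its size does.

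**2. The plan's own figures.** The documents give no figure for the responder endpoints. The arm size comes from the primary endpoint: margin 0.4, adjusted effect 0.06, SD 1.3, one-sided 2.5% and 85% power. A noncentral-t calculation gives 264 per arm (528 in total, power 85.07%), as stated in SAP 2.2.

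**3. What is known about d.** SAP 2.2 assumes that 15% will either stop randomised treatment before week 26 or lack week 26 data. Subjects treated for under 16 weeks are a subset, so under that assumption d is at most 15%, or 0.15 × 264 = 39.6 per arm. The documents do not give d itself, d by arm, or r.

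**4. Shift within an arm.** Let q be the response rate among subjects treated for at least 16 weeks.
- Treatment policy: (1 − d)q + d·r
- Under the rule: (1 − d)q
- Shift: −d·r, whatever q is

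Fall in responder rate, in percentage points (d and r assumed):

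| d | Subjects per arm (264·d) | r = 20% | r = 30% | r = 40% |
|---|---|---|---|---|
| 5% | 13.2 | 1.0 | 1.5 | 2.0 |
| 10% | 26.4 | 2.0 | 3.0 | 4.0 |
| 15% | 39.6 | 3.0 | 4.5 | 6.0 |

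**5. Shift in the contrast.** All values of d, r and q are assumed. The first three rows use q = 50% and r = 30%. The last uses r = 40% and a true rate of 45% in both arms.

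| d, arm A vs B | Treatment policy | OR | Under the rule | OR |
|---|---|---|---|---|
| 10% vs 10% | 48.0% vs 48.0% | 1.00 | 45.0% vs 45.0% | 1.00 |
| 5% vs 10% | 49.0% vs 48.0% | 1.04 | 47.5% vs 45.0% | 1.11 |
| 5% vs 15% | 49.0% vs 47.0% | 1.08 | 47.5% vs 42.5% | 1.22 |
| 12% vs 6% | 45.0% vs 45.0% | 1.00 | 40.2% vs 42.6% | 0.91 |

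Last row: 0.45 − 0.12 × 0.4 = 0.402 and 0.45 − 0.06 × 0.4 = 0.426. The odds ratio is (0.402/0.598)/(0.426/0.574) = 0.906.

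With equal d and r the difference in proportions is unchanged, but both reported rates are too low for the assigned estimand. When d or r differs so that d·r is unequal, the contrast moves as well.

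**The case against.** **The rule has a purpose.** The 16 weeks match the titration period in SAP 2.5.2. The sentence also covers the responder endpoints that require absence of hypoglycaemia. SAP 2.1 says hypoglycaemia is not systematically collected after discontinuation, so without some rule an early stopper could count as free of hypoglycaemia merely because nobody looked. This stands for those endpoints. It does not carry over to HbA1c <7% alone, whose outcome is measured or imputed after stopping.

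**No binary estimand is written out.** SAP 2.1 speaks only of a difference in change from baseline. That is correct, but SAP 3.5 and protocol 17.5.1 explicitly place the responder endpoints under that estimand, and neither declares a composite strategy.

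**It was pre-specified.** The rule was in the protocol before the SAP. That makes it planned, but not consistent with the estimand it serves.

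**The distortion is small beside sampling error.** In the 12% versus 6% example the log odds ratio is −0.099. Its unadjusted standard error is √[1/(264 × 0.402 × 0.598) + 1/(264 × 0.426 × 0.574)] = 0.177. The shift is about 0.56 standard errors, within a 95% interval of roughly 0.64 to 1.28. This stands. It is still a systematic error that the collected data can remove.

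**A reader might take 15% as the plan's stopping rate** and, spreading it evenly, put d at 0.15 × 16/26 = 9.2%. The documents do not support this. The 15% includes subjects still on treatment who only lack a week 26 value, and no timing of stops is given. A uniform r is also uncertain, since some stops follow confirmed high fasting glucose (protocol 6.5).

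**Conclusion.** The concern holds. As written, the HbA1c <7% analyses at weeks 26 and 38 do not follow the de facto estimand assigned to them. They combine a composite strategy before week 16 with treatment policy afterwards, and the plan does not say so.

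The responder rate falls by d·r in each arm: about 1–6 percentage points for d = 5–15% and r = 20–40%. The odds ratio changes modestly under unequal early stopping, as in the 0.91 instead of 1.00 example. All these sizes rest on assumed d, r and q; the documents supply only the 15% ceiling on d, under the plan's own assumption. The same subjects are overridden at week 38, though r may differ there.

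Two stronger inferences are not supported. A reader might conclude that the responder result matches no recognised strategy and cannot be interpreted. It is a readable mix of two, and the fault is that the mix is undeclared and contradicts its label. A reader might also think the trial's main conclusion is at risk. Non-inferiority rests on the continuous week 26 analysis (SAP 2.4), which does not use this rule, and the responder endpoints are supportive.

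**What to change.** In SAP 2.5.1, for the primary-estimand analysis of HbA1c <7% at weeks 26 and 38, classify each subject from the measured in-trial value (V28 or V28a; V40 or V40a), else from the imputed value, without the 16-week override. Keep the 16-week rule as a sensitivity analysis labelled as a composite strategy.

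For the responder endpoints that require no hypoglycaemia, the rule may stay, but it should be named there as a composite strategy, with the reason given.

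Record the change in SAP section 3, because the rule comes from the protocol. Declaring a composite estimand for HbA1c <7% and adding the treatment-policy analysis as a sensitivity analysis would also remove the contradiction, but would change the estimand that SAP 3.5 now names.

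The cost is a short text change, one extra model run and slightly different responder proportions. No new data are needed.

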2.5.2 Safety endpoints

Adverse events

The following endpoint on adverse events will be reported:

- Incidence of treatment-emergent adverse events (TEAEs) from baseline to week 26
- Incidence of treatment-emergent adverse events (TEAEs) during 38 weeks
- Incidence of treatment-emergent adverse events (TEAEs) during intensification period (week 26-38)

The AEs will be coded using the most recent version of the Medical Dictionary for Regulatory Activities coding.

A treatment-emergent adverse event (TEAE) is defined as an event that has onset date on or after the first day of exposure to randomised treatment and no later than seven days after the last day of randomised treatment. If the event has onset date before the first day of exposure on randomised treatment and increases in severity during the treatment period and until seven days after the last drug date, then this event should also be considered as a TEAE.

TEAEs are summarised descriptively, whereas non-treatment-emergent AE's are presented in listings. TEAE data will be displayed in terms of the number of subjects with at least one event (N), the percentage of subjects with at least one event (%), the number of events (E) and the event rate per 100 years of exposure (R).

Summaries of TEAEs and serious TEAEs will be presented as an overview including all AEs, serious AEs, number of deaths, AEs by severity, AEs by relation to treatment as assessed by the investigator and AEs of special interest including AEs leading to withdrawal and AEs leading to drug withdrawn.

Furthermore summary tables based on system organ class and preferred terms are made for:

- All TEAEs
- Serious TEAEs
- Possibly and probably related TEAEs
- Severe, moderate and mild TEAEs
- TEAEs reported by safety area of interest
- TEAEs with preferred term that are experienced by at least 5% (1%) of the subjects in any treatment arm or by at least 5% (1%) of all subjects
- TEAEs leading to withdrawal of subject or drug withdrawn

A listing of non-treatment-emergent events with onset date before the first day of exposure to randomised treatment will be presented. A listing will also be presented for non-treatment-emergent adverse events collected after the treatment-emergent period according to the definition of the TEAE.

Hypoglycaemic episodes

The definition and classification of hypoglycaemic episodes is given after the description of the statistical analysis.

Below assessments will be summarized descriptively.

- Number of nocturnal, treatment-emergent severe or BG confirmed hypoglycaemic episodes during 26 weeks
- Number of treatment-emergent severe or BG confirmed hypoglycaemic episodes during 26 weeks
- Number of nocturnal, treatment-emergent severe or BG confirmed hypoglycaemic episodes during maintenance (week 16-26)
- Number of treatment-emergent severe or BG confirmed hypoglycaemic episodes during maintenance (week 16-26)
- Number of nocturnal, treatment-emergent severe or BG confirmed hypoglycaemic episodes during 38 weeks
- Number of treatment-emergent severe or BG confirmed hypoglycaemic episodes during 38 weeks

Data on treatment-emergent hypoglycaemic episodes are presented in terms of the number of subjects with at least one event (N), the percentage of subjects with at least one event (%), the number of events (E) and the event rate per 100 years (R). Separate summaries are made by severity considering all confirmed hypoglycaemic episodes, nocturnal confirmed hypoglycaemic episodes and the ADA classification of hypoglycaemia.

In addition, to the extent where data allows, the following endpoints are analysed statistically.

During 26 weeks:

- Number of nocturnal, treatment-emergent severe or blood glucose (BG) confirmed symptomatic hypoglycaemic episodes during 26 weeks
- Number of treatment emergent severe or BG confirmed symptomatic hypoglycaemic episodes during 26 weeks
- Number of nocturnal, treatment emergent severe or BG confirmed symptomatic hypoglycaemic episodes during maintenance (week 16-26)

- Number of treatment emergent severe or BG confirmed symptomatic hypoglycaemic episodes during maintenance (week 16-26)

During 38 weeks:

- Number of nocturnal, treatment emergent severe or BG confirmed symptomatic hypoglycaemic episodes during 38 weeks
- Number of treatment emergent severe or BG confirmed symptomatic hypoglycaemic episodes during 38 weeks

For endpoints addressing the hypoglycaemic rate in the 26 weeks or the 38 weeks period, a negative binomial model will be used, including treatment, previous insulin treatment regimen, previous OAD treatment, sex, and region as factors and age as covariate. The model will use a log-link function and the logarithm of the time period in which a hypoglycaemic episode was considered treatment emergent as offset. The treatment rate ratios will be estimated and 95% confidence intervals will be calculated.

The rationale for investigating the hypoglycaemic rate during the maintenance is to reflect long term use, as prior to this period (the titration period) the glycaemic control might be unstable. For endpoints addressing hypoglycaemic rate in the maintenance period, subjects that discontinue randomised treatment during the maintenance period will contribute with the available data from the maintenance period. For subjects that discontinue randomised treatment during the 16 week titration period, the number of events in the maintenance period will be imputed based on data from the maintenance period for subjects that discontinued randomised treatment during the maintenance period. For these subjects, the number of events will be imputed corresponding to a 10 weeks maintenance period as follows:

- In the first step, 1000 samples from the posterior distribution of model parameters are extracted. The model is fitted to the on-treatment maintenance data for subjects that discontinued randomised treatment during the maintenance period for each treatment arm separately. This is done using a Bayes negative binomial log-link model with the same factors, covariates and offset as in the analyses of hypoglycaemic episodes described above. The 1000 samples are used as sampled parameter estimates in the next step.
- For each sample of model parameters, the total number of hypoglycaemic events in the maintenance period for subjects that discontinued randomised treatment in the titration period is imputed as a random number of events from a negative binomial distribution using the sampled parameters.
- For each of the 1000 imputed data sets, that now have maintenance period data for all randomised subjects, the mean treatment ratio is estimated using the same negative binomial model as in the analyses of hypoglycaemic episodes described above.

- The estimates and standard deviations for the 1000 imputed data sets are pooled to one estimate and associated standard deviation using Rubin's formula. From these the 95% confidence interval for the treatment ratio and the associated p-value are calculated.

If the above model cannot fit due to sparse data, the model in step 1 is fitted to the on-treatment data for subjects that discontinued randomised treatment during either titration or maintenance, i.e. do not complete the scheduled 26 weeks of treatment. If this model cannot fit either, factors will be left out one by-one in the model using data from all subjects discontinuing randomised treatment before week 26 in the following order, until a model fits:

- sex
- age
- region
- previous insulin treatment regimen
- previous OAD treatment

The analyses and data presentations of hypoglycaemic events will be based on the hypoglycaemic episode form.

Classification of Hypoglycaemia:

Hypoglycaemic episodes are recorded by the subjects in their trial diaries throughout the trial. The information collected includes PG before treating the episode and whether the subject was able treat him/herself. This information is used by Novo Nordisk to classify episodes according to the confirmed hypoglycaemia definition and the ADA definition (severe, documented symptomatic, asymptomatic, probably symptomatic and pseudo).

- Treatment-emergent: hypoglycaemic episodes will be defined as treatment-emergent if the onset of the episode occurs on or after the first day of trial product administration, and no later than 7 calendar days after the last day on trial product
- Nocturnal hypoglycaemic episodes: episodes occurring between 00:01 and 05.59 both inclusive.
- Hypoglycaemic episodes are classified according to the Novo Nordisk classification of hypoglycaemia (see [Figure 2-1](#)) and the ADA classification of hypoglycaemia (see [Figure 2-2](#)).

[figure not shown]
Novo Nordisk classification of hypoglycaemia

In normal physiology, symptoms of hypoglycaemia occur below a plasma glucose level of 3.1 mmol/L (56 mg/dL)⁴. Therefore, Novo Nordisk has included hypoglycaemia with plasma glucose levels below this cut-off point in the definition of BG confirmed hypoglycaemia.

Novo Nordisk uses the following classification (see [Figure 2–1](#)) in addition to the ADA classification:

- Severe hypoglycaemia according to the ADA classification⁵
- Symptomatic BG confirmed hypoglycaemia: An episode that is BG confirmed by plasma glucose value <3.1 mmol/L (56 mg/dL) **with** symptoms consistent with hypoglycaemia.
- Asymptomatic BG confirmed hypoglycaemia: An episode that is BG confirmed by plasma glucose value <3.1 mmol/L (56 mg/dL) **without** symptoms consistent with hypoglycaemia.
- Severe or BG confirmed symptomatic hypoglycaemia: An episode that is severe according to the ADA classification⁵ or BG confirmed by a plasma glucose value <3.1 mmol/L (56 mg/dL) **with** symptoms consistent with hypoglycaemia.
- BG confirmed hypoglycaemia: An episode that is BG confirmed by a plasma glucose value <3.1 mmol/L (56 mg/dL) **with** or **without** symptoms consistent with hypoglycaemia.

Severe or BG confirmed hypoglycaemia: An episode that is severe according to the ADA classification⁵ or BG confirmed by a plasma glucose value <3.1 mmol/L (56 mg/dL) **with** or **without** symptoms consistent with hypoglycaemia

[figure not shown]
Note: Glucose measurements are performed with capillary blood calibrated to plasma equivalent glucose values

Figure 2–1 Novo Nordisk classification of hypoglycaemia

ADA classification⁵ of hypoglycaemia

- Severe hypoglycaemia: An episode requiring assistance of another person to actively administer carbohydrate, glucagon, or take other corrective actions. Plasma glucose concentrations may not be available during an event, but neurological recovery following the return of plasma glucose to normal is considered sufficient evidence that the event was induced by a low plasma glucose concentration.
- Asymptomatic hypoglycaemia: An episode not accompanied by typical symptoms of hypoglycaemia, but with a measured plasma glucose concentration $\leq 3.9 \text{ mmol/L (70 mg/dL)}$.
- Documented symptomatic hypoglycaemia: An episode during which typical symptoms of hypoglycaemia are accompanied by a measured plasma glucose concentration $\leq 3.9 \text{ mmol/L (70 mg/dL)}$.
- Pseudo-hypoglycaemia: An episode during which the person with diabetes reports any of the typical symptoms of hypoglycaemia with a measured plasma glucose concentration $> 3.9 \text{ mmol/L (70 mg/dL)}$ but approaching that level.

- Probable symptomatic hypoglycaemia: An episode during which symptoms of hypoglycaemia are not accompanied by a plasma glucose determination but that was presumably caused by a plasma glucose concentration ≤ 3.9 mmol/L (70 mg/dL).

Note: Glucose measurements are performed with capillary blood calibrated to plasma equivalent glucose values

Figure 2–2 ADA classification of hypoglycaemia

Insulin dose

- Total insulin dose at week 26
- Total insulin dose at week 38

Observed values of total insulin dose at week 26 and week 38 will be summarised by the arithmetic mean, SD, median, and minimum and maximum value. Separate summaries will also be made for the basal insulin dose and the bolus insulin dose.

Weight

- Change in weight from baseline to week 26
- Change in weight from baseline to week 38

are summarised descriptively and analysed statistically using the primary statistical analysis for the primary estimand.

The following safety assessments will be reported:

Clinical evaluations at week 26 and week 38

- Physical examination
- Vital signs (blood pressure and pulse)
- Dilated fundoscopy or fundus photography
- 12-lead electrocardiogram

will be summarised descriptively including:

- Change from baseline to week 26
- Change from baseline to week 38

Any findings in the physical examination evaluation at screening will be presented as listings. Any clinically significant deterioration of a pre-existing condition after the screening visit, as well as any new clinically findings will be recorded as adverse events.

Laboratory assessments

- Haematology (haemoglobin, haematocrit, erythrocytes, thrombocytes, leucocytes)
- Biochemistry (creatinine, ALT, AST, AP, sodium, potassium, albumin, total bilirubin)
- Insulin antibodies

All laboratory parameters will be summarised descriptively.

The following tables will be presented based on observed data:

- Shift tables from baseline to week 26
- Shift tables from baseline to week 38
- Change from baseline to week 26
- Change from baseline to week 38
- Proportion of subjects with measurements outside reference range by treatment and week.

For each laboratory parameter, individual values outside the reference range (abnormal values) will be listed.

